13.2. Laboratory Evaluations

Clinical laboratory data of local laboratories will be presented in separate tables for each laboratory test type (hematology, blood chemistry, coagulation, urinalysis). Each laboratory parameter will be presented with the number and percentage of patients with values below, within, or above the normal range at each time point by treatment group and overall. Additionally, a shift table of the number and percentage of patients with values below, within, or above the normal range at each time point by treatment group and overall. Additionally, a shift table of the number and percentage of patients with normal and abnormal, and clinically significant abnormal values at each scheduled post-baseline visit compared to the normal, abnormal, and clinically significant abnormal categorization at baseline will be provided by treatment group. A listing of clinically significant abnormal values will be provided in the tables section.

Summary tables of actual values and changes from baseline can be presented for continuous laboratory parameters only after 'normalization' of the local laboratory assessment as supposed by Chuang-Stein (see reference 1 and 2) using one reference laboratory based on the following formula

$$s = L_s + (x - L_x) \frac{U_s - L_s}{U_x - L_x}$$

where s = the transformed individual laboratory value considering the normal range of the reference laboratory, x = the original laboratory value, L_x and U_x are the lower and upper limits or normal range of the local laboratory for the respective parameter, L_s and U_s are the lower and upper limits of the selected reference laboratory. For calculating summary statistics, results of <x or <=x will be imputed as x/2 and results of >x or >=x will be imputed as x.

Pregnancy test results will be listed only for randomized female patients.

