8.1. General Methods

SAS® version 9.4 or higher will be used for all statistical analyses and tabulations.

In general, summaries will present data by treatment group and overall for each scheduled assessment time where appropriate. Efficacy, PK and PD summaries will be presented by treatment group, only.

Unless stated otherwise, descriptive summaries will be presented as follows: Continuous and ordinal variables will be summarized by the number of patients (N), mean, standard deviation, median, minimum, and maximum for actual values and change from baseline. Additionally, for ordinal data, the number and percentage of patients in each category will be presented. Binary and categorical variables will be summarized by treatment group by presenting the number and percentage of patients in the categories.

Statistical tests for comparison between treatments for all defined estimands and endpoints of efficacy will be performed using a two-sided alpha level of 10%. No adjustment for multiple testing will be applied in this descriptive proof-of-concept study. Additionally, 95% confidence intervals will be provided.

Adverse events and medical history will be coded according to the most recent version of Medical Dictionary for Regulatory Activities (MedDRA). Prior and concomitant medications will be coded using the most recent WHO Drug Dictionary version. The actual version of MedDRA and WHO drug used will be noted in the footnote of the respective output. Unless otherwise specified, summaries will be presented for each treatment and overall.

If there are multiple assessments collected for the same scheduled time, the last available assessment before start of study treatment will be used as baseline value and the first assessment at the respective post-baseline visit will be used for post-baseline summarization, except for COVID-19 test results where the last assessment at the post-baseline visit will be used for post-baseline summarization.

All relevant patient data will be included in listings. All patients entered into the database will be included in patient data listings.

Data collected at unscheduled visits will be included in the data listings but will not be included in the analyses or in treatment summaries except unscheduled COVID-19 test results.

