13.1. Adverse Events / Adverse Drug Reactions

All AEs will be coded using the most recent MedDRA Version.

Each AE will be assigned a grade which refers to the severity of the AE based on the Common Terminology Criteria for Adverse Events version 5.0. The Common Terminology Criteria for Adverse Events v5.0 displays grades 1 through 5 with unique clinical descriptions of the severity for each AE. Tables for the classification of the AE severity and relationship to the drug are provided in Tables 6 and 7 in Section 12.6.1 of the protocol.

When changes in the severity of an AE occur more frequently than once a day, the maximum severity for the event should be noted in the eCRF. If the severity category changes over a number of days, then those changes should be recorded separately (with distinct onset dates) in the eCRF: the assessment of an AE in several records will be called as 'episodes' of one AE.

A treatment-emergent AE (TEAE) is an AE that starts or worsens at any time after initiation of study drug until the end of the follow-up period at Day 60. Events with missing onset dates will be considered as TEAEs. If a patient experiences >1 occurrence of the same AE, the occurrence with the greatest severity and the closest association with the study drug will be used in the corresponding summary tables. In case that for one AE, several AE episodes with eg changing severity are reported, an aggregation of all respective episodes to one AE will be performed prior to summarization. The worst severity and the worst relationship will be assigned to the aggregated AE.

Listings presenting all AEs including all episodes of one AE will be produced for TEAEs and non-TEAEs with the flagging of SAEs. Listings of serious TEAEs, TEAEs leading to study drug withdrawal, and TEAEs leading to death will be presented in the table section of the outputs. Additionally, in the listing TEAEs starting in the treatment period and TEAEs starting in the follow-up period or starting after the initial treatment has stopped will be flagged

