13.5. Physical Examination

Abnormal physical examination results will be summarized by presenting number and percentage of patients for each body system by treatment group and overall for all scheduled visits. All physical examination data will be listed for the randomized patients.

This document is confidential.

SAP Text Version: 2.0, 31-Aug-2022 Controlled Document ID: CC , Effective Date 31-Aug-2020 Filing requirements: TMF

Page 46 of 56

14. Health Economics

Not applicable.

This document is confidential.

SAP Text Version: 2.0, 31-Aug-2022 Controlled Document ID: CC , Effective Date 31-Aug-2020 Filing requirements: TMF

Page 47 of 56

15. Interim Analyses or IDMCs

There will be no interim analysis in the study.

An independent DMC will be established by the sponsor or designee to review accumulating study data at regular intervals (as per the DMC charter) throughout the study to ensure the safety of patients and review overall study conduct. Additional data may be reviewed that are related to efficacy, but the DMC will only be reviewing data for risk-benefit purposes. Members will include experts in drug safety and/or medical specialist and biostatistics, who are not participating in this study and do not have affiliation with the investigators or the sponsor. The DMC can recommend in writing to the sponsor whether to continue, modify, or stop the clinical study on the basis of safety considerations. The pre-specified study stopping rules for the trial are defined as follows:

- death (not including disease progression) in any patient in whom the cause of death is judged to be related to the study drug by investigator
- the occurrence in any patient of a SAE whose causal relationship (ie, without a plausible alternative explanation) to the study drug is judged to be related by investigator
- two occurrences of a clinically significant Grade 3 or higher laboratory abnormality assessed to be related to the study drug by investigator.

The DMC's specific duties will be fully described in a DMC charter. The list of the outputs that will be produced for the DMC will be attached to the charter. An unblinded team from Syneos Health Biostatistics will perform the analyses as described in Section 4.4 of this SAP to maintain the blinding of the study.

This document is confidential.

16. Changes from Analysis Planned in Protocol

Not applicable

This document is confidential.

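### No laboratory table in SAP Section 13.2 is graded, so same-direction worsening from an abnormal baseline moves no shift-table cell unless it is labelled clinically significant

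*SAP*

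**What the plan says.** SAP Section 13.2 names these laboratory displays, based on local laboratory data:

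- Range counts by time point: "Each laboratory parameter will be presented with the number and percentage of patients with values below, within, or above the normal range".
- A directional shift, announced as "a shift table of the number and percentage of patients with values below, within, or above the normal range at each time point". As it reads, the sentence has no verb and names no baseline comparison.
- A three-level shift: "a shift table of the number and percentage of patients with normal and abnormal, and clinically significant abnormal values at each scheduled post-baseline visit". Its baseline axis uses the same three levels, again without direction or grade.
- A separate listing of the values labelled clinically significant.
- Continuous summaries, on a condition: "Summary tables of actual values and changes from baseline can be presented for continuous laboratory parameters only after 'normalization' of the local laboratory assessment". Under Section 8.1, continuous variables are summarized by "mean, standard deviation, median, minimum, and maximum for actual values and change from baseline".

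Grades appear elsewhere in the SAP. Section 13.1 grades adverse events by the "Common Terminology Criteria for Adverse Events version 5.0". One of the stopping rules in Section 15 is "two occurrences of a clinically significant Grade 3 or higher laboratory abnormality assessed to be related to the study drug by investigator".

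**The concern.** Patients hospitalized with moderate to severe COVID-19 can be expected to enter with some laboratory values out of range. For those patients and analytes, a shift table that separates only normal from abnormal has nowhere to put further worsening. The single step left is the label of clinical significance. Section 13.2 gives it no numeric threshold, and it would be applied across about 40 sites. At stake is whether the final safety tables can show, by arm and on a common scale, how many patients had a marked laboratory deterioration. The plan already works with grades for adverse events and in a stopping rule, so their absence from the laboratory tables stands out.

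**Working it through.** The SAP gives no figure on this point, so there is nothing to reproduce. The check is to pass example values through the planned categories.

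**Inputs.** The categories come from Section 13.2. The normal range of 10 to 40 and the patient values are assumptions chosen for illustration, with the local range equal to the reference range. 'Abnormal' is taken to mean outside the normal range. No value is labelled clinically significant.

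| Baseline to post-baseline | Multiple of upper limit (value / 40) | Three-level shift | Range categories |
|---|---|---|---|
| 44 to 80 | 1.1 to 2 | abnormal to abnormal | above to above |
| 44 to 200 | 1.1 to 5 | abnormal to abnormal | above to above |
| 44 to 400 | 1.1 to 10 | abnormal to abnormal | above to above |
| 5 to 200 | below range to 5 | abnormal to abnormal | below to above |

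The first three rows change no cell in either kind of table. The fourth changes a cell only in a directional shift, if one is produced.

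**Can the continuous summaries fill the gap?** Section 13.2 normalizes by s = Ls + (x − Lx)(Us − Ls)/(Ux − Lx). With equal ranges s = x, so the rise from 44 to 400 is a change of 400 − 44 = 356.

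- Its effect on the arm mean, all other patients being unchanged, is 356/80 = 4.45 in an arm of 80 and 356/40 = 8.9 in an arm of 40.
- It could appear in full as the maximum change. The maximum shows one extreme value and does not say how many patients worsened.
- Normalization need not preserve multiples of the upper limit. With an assumed local range of 10 to 40 and reference range of 0 to 40, x = 400 gives s = 0 + (400 − 10)(40 − 0)/(40 − 10) = 390 × 40/30 = 520. That is 520/40 = 13 times the reference upper limit, against 10 times the local one.
- Section 13.2 sets results reported as above x equal to x, which truncates the highest values.
- The wording is permissive, whereas Section 13.3 commits to the corresponding summaries for vital signs.

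**Other routes.** Section 8.1 lists all relevant patient data, but a listing does not compare arms. A laboratory worsening reported as an adverse event is graded and, under Section 13.1, tabulated by maximum intensity and arm. That captures only what is reported as an event.

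**The case against.** The strongest reply is that the laboratory plan is wider than the one shift table. Section 13.2 also has directional range counts, a sentence announcing a directional shift, and normalized change summaries for which the formula and the imputation of censored results are already fixed. 'Can be presented only after normalization' may well state a precondition and not an option. Reported laboratory events are graded in the adverse event tables. For a proof-of-concept study of about 120 patients, a grade shift could be called a matter of table design.

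Much of this stands, and it rules out several stronger readings that a reader might infer.

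- *That the laboratory plan has no direction.* This is true of the three-level shift only. The directional sentence may be a drafting slip or an artefact of text extraction, but it cannot be ignored.
- *That a large worsening shows only if an investigator calls it significant.* This is true of the shift tables, not of the whole plan. Section 13.2 also does not say who assigns the label; that it is the investigator is an inference.
- *That 13.2 contradicts the stopping rule, or that the monitoring committee would not see graded data.* The rule in Section 15 requires clinical significance and investigator-judged relatedness as well as grade, so a grade table alone would not display it. The committee's outputs are listed in its charter, which is not at hand.
- *That a known number of patients is lost to view.* Under an assumption of 30 to 60% abnormal at baseline for an analyte, 24 to 48 of 80 and 12 to 24 of 40 patients would start out of range. These figures restate the assumption, and the SAP has no data to support it.

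What survives is narrower: none of the other displays counts, by arm, the patients who worsened by an objective laboratory criterion.

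**Conclusion.** The point holds as a gap in the safety tables, not as an error or contradiction. No laboratory table in Section 13.2 is graded. Same-direction worsening from an abnormal baseline changes no shift-table cell unless it is labelled clinically significant, and the label has no numeric criterion there. This follows from the stated categories, taking abnormal to mean outside the normal range; the worked values only illustrate it. How many patients it touches depends on the share out of range at baseline, which the SAP does not give. The efficacy analyses are unaffected. The improvement is worth making because it is cheap and the SAP already names the grading system.

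**What to change.** In Section 13.2, add a shift table by treatment group from baseline grade to worst post-baseline CTCAE v5.0 grade, separately for low and high values, for analytes with numeric CTCAE criteria. List those analytes. State whether unscheduled values count towards the worst grade, since Section 8.1 otherwise keeps unscheduled data out of the summaries.

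For the remaining analytes, complete the below/within/above sentence as a baseline-to-post-baseline shift by arm, after checking it against the source file. Keep the clinically significant shift and the listing. Leave the stopping rule in Section 15 unchanged.

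The cost is SAP wording, programming of the grades and larger tables. The normalization formula already needs the local lower and upper limits, so little or no new data should be required. That should be confirmed analyte by analyte, because the SAP does not show what each grade needs.

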13.3. Vital Signs

Vital signs will include systolic blood pressure (mmHg), diastolic blood pressure (mmHg), heart rate (beats per minute, bpm), respiration rate (breaths per minute), SpO₂, and body temperature (°C). Summary tables of the actual values and changes from baseline will be provided for each vital sign parameter at each scheduled visit by treatment group, and in total.

Additionally, body weight and BMI will be summarized with actual values and change from baseline at each scheduled visit by treatment group, and in total.

Vital signs data, body weight and BMI will be listed for randomized patients.

13.4. ECG

The overall interpretation of ECG at screening will be summarized by treatment group and overall and listed for all randomized patients.

This document is confidential.

SAP Text Version: 2.0, 31-Aug-2022 Controlled Document ID: CCC , Effective Date 31-Aug-2020 Filing requirements: TMF

Page 45 of 56

13.5. Physical Examination

Abnormal physical examination results will be summarized by presenting number and percentage of patients for each body system by treatment group and overall for all scheduled visits. All physical examination data will be listed for the randomized patients.

This document is confidential.

SAP Text Version: 2.0, 31-Aug-2022 Controlled Document ID: CC , Effective Date 31-Aug-2020 Filing requirements: TMF

Page 46 of 56

14. Health Economics

Not applicable.

This document is confidential.

SAP Text Version: 2.0, 31-Aug-2022 Controlled Document ID: CC , Effective Date 31-Aug-2020 Filing requirements: TMF

Page 47 of 56

15. Interim Analyses or IDMCs

There will be no interim analysis in the study.

An independent DMC will be established by the sponsor or designee to review accumulating study data at regular intervals (as per the DMC charter) throughout the study to ensure the safety of patients and review overall study conduct. Additional data may be reviewed that are related to efficacy, but the DMC will only be reviewing data for risk-benefit purposes. Members will include experts in drug safety and/or medical specialist and biostatistics, who are not participating in this study and do not have affiliation with the investigators or the sponsor. The DMC can recommend in writing to the sponsor whether to continue, modify, or stop the clinical study on the basis of safety considerations. The pre-specified study stopping rules for the trial are defined as follows:

- death (not including disease progression) in any patient in whom the cause of death is judged to be related to the study drug by investigator
- the occurrence in any patient of a SAE whose causal relationship (ie, without a plausible alternative explanation) to the study drug is judged to be related by investigator
- two occurrences of a clinically significant Grade 3 or higher laboratory abnormality assessed to be related to the study drug by investigator.

The DMC's specific duties will be fully described in a DMC charter. The list of the outputs that will be produced for the DMC will be attached to the charter. An unblinded team from Syneos Health Biostatistics will perform the analyses as described in Section 4.4 of this SAP to maintain the blinding of the study.

This document is confidential.

16. Changes from Analysis Planned in Protocol

Not applicable

This document is confidential.

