- g. Medical/surgical medical history includes all active and chronic diseases (eg, asthma and COPD), and any diseases diagnosed in the past 1 year (before screening) that the investigator considers clinically significant. Additional pre-existing conditions present at the time when informed consent is given and up to the time of first dosing (Day 1) are to be regarded as concomitant. Medical history will include documentation of social behaviors, including use of tobacco, nicotine (including use of electronic cigarettes), and soft or hard drugs (including cannabis), as well as alcohol consumption, if applicable. Smoking history also must be documented as part of medical history and includes: never, light (<100 cigarettes/lifetime), active smoker, and former smoker (quit date). History of number packs/day, number of smoking years, and quitting time for former and active smokers must also be documented. Additionally, the investigators will document at screening the patient's Charlson score via the Charlson Comorbidity Index (see Section 12.1 of protocol for further details).

- h. A complete physical examination will be performed at screening. Physical examinations will be performed by a physician, nurse, or other appropriately trained staff. The complete physical examination includes: head, eyes, ears, nose, and throat; heart; lungs; abdomen; skin; cervical and axillary lymph nodes; and neurological and musculoskeletal systems. A limited physical examination to verify continued patient eligibility and to follow-up regarding any change in medical history will be performed at the visits indicated above. Symptom-driven, limited physical examinations may be performed as clinically indicated during the study (according to SoC).
- i. Vital signs include systolic and diastolic blood pressure, heart rate, respiration rate, SpO₂, and body temperature. All vital signs will be measured after the patient has been resting for at least 5 minutes. Blood pressure measurements are to be taken in the same arm for the duration of the study. Moreover, additional vital signs may be performed as needed in case of any cardiac AE.
- j. For patients who remain hospitalized only.
- k. A 12-lead, resting ECG will be obtained locally at screening. At screening, the investigator must examine the ECG traces for clinically significant abnormalities that could exclude the patient from the study. ECGs should always be obtained in supine position after adequate rest (≥5 minutes).

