5.7. Safety Endpoints

- Safety and tolerability assessed by:
 - Cumulative incidence of treatment-emergent AEs (summarized by seriousness, severity, relationship to the study medication, outcome, and duration)
 - Vital sign parameters
 - o Clinical laboratory parameters
 - Physical examination findings

This document is confidential.

Page 25 of 56

6. Analysis Sets

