18.2.5.2. Table Conventions

- Units will be included where available
- For categorical parameters, all categories will be presented in the table, even if n=0 for all treatment groups in a given category. For example, the frequency distribution for symptom severity would appear as:

Severity Rating	N
severe	0
moderate	8
mild	3

- Where percentages are presented in these tables, zero percentages will not be presented and so counts of 0 will be presented as 0 and not as 0 (0%).
- An Unknown or Missing category will be added to each parameter for which information is not available for 1 or more patients
- Unless otherwise specified, the estimated mean and median for a set of values will be printed out to 1 more significant digit than the original values, and standard deviations will be printed out to 2 more significant digits than the original values. The minimum and maximum will report the same significant digits as the original values. For example, systolic blood pressure will be presented as follows:

•	N	•	XX
•	Mean	•	XXX.X
•	Std Dev	•	X.XX
•	Median	•	XXX.X
•	Minimum	•	XXX
•	Maximum	•	XXX

- P-values will be output in the format: '0.xxx', where xxx is the value rounded to 3 decimal places. Every p-value less than 0.001 will be presented as <0.001. If the p-value are less than 0.0001, then present as <0.0001. P-values above 0.999 will be presented as >0.999
- Percentage values will be printed to one decimal place, in parentheses with no spaces, one space after the count (eg, 7 (12.8%), 13 (5.4%)). Unless otherwise noted, for all percentages, the number of patients in the analysis set for the treatment group who have an observation will be the

This document is confidential.

SAP Text Version: 2.0, 31-Aug-2022 Controlled Document ID: CCC, Effective Date 31-Aug-2020 Filing requirements: TMF

Page 53 of 56

denominator. Percentages after zero counts will not be displayed and percentages equating to 100% will be presented as 100%, without decimal places

- Tabular display of data for medical history, prior/concomitant medications, and all tabular displays
 of adverse event data will be presented by the body system, treatment class, or SOC with the
 highest occurrence in the active treatment group in decreasing order, assuming all terms are
 coded. Within the body system, drug class and SOC, medical history (by preferred term), drugs (by
 ATC1 code), and adverse events (by preferred term) will be displayed in decreasing order. If

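### SAP 13.5 reports physical-examination abnormalities only as per-visit counts, with no baseline-referenced summary to separate new from pre-existing findings

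*SAP*

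**What the plan says.** SAP 5.7 lists "Physical examination findings" among the safety endpoints. Section 13.5 gives the whole analysis: "Abnormal physical examination results will be summarized by presenting number and percentage of patients for each body system by treatment group", with the table made "by treatment group and overall for all scheduled visits". It adds a patient listing: "All physical examination data will be listed for the randomized patients". It names no shift table, change from baseline or count of new abnormalities. The general default for categorical variables in 8.1 is numbers and percentages per category, so it adds none.

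The examinations differ in scope. Footnote h to Table 1 (section 4.6) says "A complete physical examination will be performed at screening" and then "A limited physical examination to verify continued patient eligibility and to follow-up regarding any change in medical history will be performed" at the later visits marked in the table. These are Day 1, Day 8, Day 14, Day 28 and discharge or early termination. Under footnote s, the Day 8 examination is routine only for patients still in hospital. Under footnote e, an assessment that cannot be done at a remote Day 14 or Day 28 visit may be missed without counting as a deviation. Under footnote a, Day 1 procedures need not be repeated if screening was on the same day.

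The default percentage denominator in 18.2.5.2 is "the number of patients in the analysis set for the treatment group who have an observation".

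**The concern.** The safety question is whether more patients develop a new abnormality on MP1032 than on placebo. A prevalence count at each visit answers a different question, because a finding present at entry and a finding that arose on treatment add equally to the total. In patients admitted with moderate to severe COVID-19, abnormal findings at entry are to be expected.

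The SAP handles its comparable data differently. Section 13.2 plans a laboratory shift table against the baseline category, 13.3 plans change from baseline for vital signs, weight and BMI, and 10.4 plans shift tables for each COVID-19 symptom. ECG is recorded only at screening. Among the safety assessments repeated on schedule, the physical examination alone has no reference to baseline, although 8.2 already defines one. At stake is how readable one safety output is, not the trial's conclusions on efficacy.

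**Working it through.** The SAP gives no figure on this point, so there is none to reproduce. The counts below are assumptions, apart from the planned arm sizes of 80 and 40 (section 4.3).

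**1. What per-visit totals reveal about new cases.** Let N patients in one arm be examined for the same body system at baseline and at a later visit, with B abnormal at baseline and L abnormal later. New cases are L minus those abnormal at both visits. That overlap is not reported. It can be at most the smaller of B and L, and at least max(0, B + L − N). So:

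- fewest new cases = max(0, L − B)
- most new cases = min(L, N − B)

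With N = 80:

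| B | L | Fewest new | Most new | As % of 80 | As % of those normal at baseline |
|---|---|---|---|---|---|
| 16 | 16 | max(0, 0) = 0 | min(16, 64) = 16 | 0 to 20 | 0 to 25 (of 64) |
| 16 | 20 | max(0, 4) = 4 | min(20, 64) = 20 | 5 to 25 | 6.3 to 31.3 (of 64) |
| 8 | 8 | max(0, 0) = 0 | min(8, 72) = 8 | 0 to 10 | 0 to 11.1 (of 72) |
| 0 | 8 | max(0, 8) = 8 | min(8, 80) = 8 | 10 | 10 (of 80) |

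The totals fix the number of new cases in special situations only, such as no abnormality at baseline. Otherwise they give a range, which can be wide.

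**2. When the patients examined change.** The bounds assume the same patients at both visits. Suppose the 16 patients abnormal at baseline all stay in hospital to Day 8 and some of the other 64 are discharged and not examined. The Day 8 figure is then 16 out of fewer than 80. That is above 20% and looks like a rise, with no new case at all.

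**3. Whether a baseline exists.** Section 8.2 takes the most recent recorded pre-dose value. Applied per body system, a system not covered by the limited Day 1 examination keeps its value from the complete screening examination. A baseline status should therefore be available for nearly every patient and system.

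**4. Two size checks on assumed rates.**

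- Chance difference between arms at entry: 1.96 × sqrt(p(1 − p)(1/80 + 1/40)). For p = 0.30, 0.60 and 0.80 this is ±17.4, ±18.6 and ±15.2 percentage points.
- Difference in new abnormalities, 10% against 5%, if all 80 and 40 were normal at baseline: SE = sqrt(0.09/80 + 0.0475/40) = 0.048, a 95% margin of ±9.4 points.

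**The case against.** The strongest reply is that 13.5 follows the SAP's own default for categorical data, contradicts nothing, and that the plan has other ways to see new findings. Much of this stands, and it rules out several stronger readings that a reader might infer.

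- **That the plan cannot show new abnormalities.** This is too absolute. The screening rows appear in the same output, the placebo column gives a concurrent comparison, and a net rise in the same patients gives a lower bound. All examination data are listed. A finding reported as an adverse event that starts or worsens after the first dose enters the TEAE tables (13.1).
- **That complete and limited examinations are pooled into one count.** The summary is by scheduled visit, and nothing in the SAP pools them.
- **That later examinations happen only because something changed.** Footnote h makes the limited examinations scheduled. The symptom-driven ones are a separate provision, and 8.1 keeps unscheduled data out of summaries. Which systems a limited examination covers is not in the SAP and may be in the protocol, so no claim about tiny denominators for one system can rest on it.
- **That missing examinations are hidden.** Section 18.2.5.2 adds an unknown-or-missing category wherever information is lacking.
- **That chance imbalance at entry will pass for harm.** The margins of 15 to 19 points rest on assumed prevalences, and the screening rows would display such an imbalance.

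What the reply does not supply is the missing summary. The TEAE route depends on the investigator reporting the finding as an adverse event, and a listing is not a summary of an endpoint.

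**Conclusion.** The point holds as a minor gap in safety reporting. For a named safety endpoint, 13.5 gives per-visit prevalence only, and that does not in general separate new from pre-existing abnormalities. The width of the ambiguity depends on how common abnormality is at entry, which the SAP does not state. It is nil if no one is abnormal at baseline and 0 to 16 new cases in the 16-then-16 illustration. Changes in who is examined, at Day 8 and at remote visits, widen it further.

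The gain should not be oversold. A shift table gives the number of newly abnormal patients among those examined at both times. With 80 and 40 patients, however, a 5-point excess would still lie within a margin of about 9 points, so the output stays descriptive. The primary and key secondary analyses and the sample size are untouched.

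**What to change.** In 13.5, keep the existing table and listing and add one output on the Safety Set, per body system and treatment arm:

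- a shift table of baseline status under the 8.2 definition (normal, abnormal, not examined) against status at each scheduled post-baseline visit, in the same three categories;
- the number and percentage of newly abnormal patients, with one stated denominator: patients normal at baseline and examined for that system at that visit;
- the not-examined count for each visit and arm, so that the effect of discharge and remote visits can be seen.

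The cost is one revised table shell and a slightly longer table, from data already collected. No visit or assessment changes. The table does not remove selection in who is examined after baseline; it only makes it visible.
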